Official Study Title: Capsaicin 8% Patch for Spinal Cord Injury Neuropathic Pain

NCT number: NCT02441660

IRB Approval Date: 07.24.2019

Unique Protocol ID: HSC20150322H

Protocol Template Form

Item 1 UTHSCSA	15-322H
Tracking Number	

Item 2 Abstract / Project Summary

Provide a succinct and accurate description of the proposed research. State the purpose/aims. Describe concisely the research design and methods for achieving the stated goals. This section should be understandable to all members of the IRB, scientific and non-scientific.

DO NOT EXCEED THE SPACE PROVIDED.

Purpose/Objectives: Current pharmacologic agents for neuropathic pain (NP) in Spinal Cord Injury (SCI) provide 20-30% pain reduction at best; so there is clear need for research studies on new promising evidence-based therapeutic agents. Animal spinal cord injury models show the Transient Receptor Potential Vanilloid subfamily, member 1 (TRPV1) defunctionalization with capsaicin decreases nociceptor hyperactivity. Human trials are needed to substantiate this effect. Most systemic effects of oral agents often limit tolerability, especially as doses are titrated up to achieved maximum clinical effect. Analgesics that can be applied topically have the potential to largely overcome this problem; the only published study of a topical analgesic in persons with SCI examined low dose capsaicin cream in 8 SCI persons and found efficacy. Thus more studies on topical analgesics are needed in persons with SCI. We propose to conduct the first prospective trial of Capsaicin 8% (C8P) in persons with SCI, with hopes to provide SCI patients and clinicians with evidence for a much-needed alternative topical therapeutic without the systemic effects that often limit tolerability.

Research Design/Plan: Randomized dual balanced 2-sequence 2-treatment, 2-period (each period is 12 weeks long), crossover study; with an additional prospective trial arm

Methods:

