Capsaicin 8% patch (Qutenza) is an FDA approved treatment for neuropathic pain in post herpetic neuralgia (PHN). After the FDA approval of Qutenza several studies have been published assessing the efficacy and safety in patients with HIV autonomic neuropathy and PHN. In a meta-analysis examining 2057 persons with PHN and HIV-AN, the proportion of responders with relief (>30% improvement in pain lasting from 2-12 weeks) over a 12-week treatment period was 43% in the C8P group and 34% in the control group, a statistically significant difference.

A retrospective review by [name] and [name] pending publication in the American Journal of Physical Medicine and Rehabilitation also supports that Capsaicin 8% patch provided all three patients in the study had complete relief of pain on average after 2 weeks for an average duration of 169 days.

relation to your protocol.	
Item 4	While low dose capsaicin cream has shown efficacy with minimal side effects in radicular pain of 8 SCI
Purpose and rationale Insert purpose, objectives and research questions/hypotheses here. If you cut and paste from another document, make	persons, short dosing intervals (every 1-4 hours) and poor manual dexterity of persons with SCI (e.g., tetraplegia) can impair efficacy and adherence. Thus the novelty of high dose capsaicin is that a single topical application of the C8P for only 1 hour could potentially provide pain relief for 8-12 weeks.
sure the excerpted material answers the question	

Item 5 Study Population(s) Being Recruited In your recruitment plan, how many different populations of prospective subjects do you plan to target? Provide number: 2 e.g., a population can be individuals with type 2 diabetes controlled with diet and/or a population of healthy controls. Or a population can be individuals attending an education program, etc. List each different population on a separate row and provide a short descriptive label: (e.g., normal-healthy, diabetics, parents, children, etc.) To add rows use copy & paste	Identify the criteria for inclusion :	Identify the criteria for exclusion : 4.

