RCT: Pre-study data including subjective description of pain, baseline VAS, LANNS and NPRS. Pre-study data collection will include an intake form with subjective description of pain, baseline VAS / LANNS/NPRS, a numerical scale such as SF36 that measures quality of life parameters, subjective FIM scores, and pain diagrams will be obtained on each participant via the outpatient spinal cord injury clinic, or inpatient spinal cord injury unit.

Substudy: Non randomized, non-controlled arm: no pre-study data collection.

RANDOMIZATION: (RCT only)

Randomized dual balanced 2-sequence 2-treatment, 3-period, crossover study (see Table 1).

Tale 1. The proposed study layout

	Period	
Sequence	1	2
1	Α	В
2	В	Α

Where A indicates 8% Capsaicin and B indicates Low dose capsaicin control patch [1]. Each treatment period will be 12 weeks in duration. The proposed design is a standard 2-period, 2-treatment, 2-sequence design. Inclusion criteria: >1year post SCI, chronic neuropathic pain with VAS>3, pain below the level of injury and failure of at least 3 oral or topical pharmacological agents. Exclusion criteria: painful area >1120cm² (4 patches), skin breakdown over area and uncontrolled hypertension.

Methods:

RCT: Each participant will be randomized to one of two sequences:

Sequence 1: C8P application followed by one reapplication of a low dose capsaicin control patch (0.025% Well Patch) (available over the counter)

ÒR

Sequence 2: Control patch (0.025% Well Patch) followed by one replication of C8P, as indicated in Table 1.

Patch application method: Per manufacturers' application directions, the painful area will be treated with topical lidocaine

2.5%/prilocaine 2.5% for 1 hour prior to application of the test patch(es). Active and control patches will then be applied and left in place for one hour. After removal, the cooling gel will be applied to decrease any burning sensation from the capsaicin, per manufacturers' protocol. Blood pressure will be monitored every 30minutes after the capsaicin (control or treatment) patch over the hour of application.

Substudy: Non-randomized, non-controlled prospective arm: Patients with SCI undergoing patch as routine medical treatment for refractory neuropathic pain will be recruited and enrolled immediately after patch application. Subsequently, they will be followed for a 12 week period using the identical protocol of data collection post patch application in the RCT, without reapplication of a control patch.

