Post patch application data collection (RCT and substudy): Measurements of the primary outcome (VAS) will occur every 2 weeks and all secondary outcomes will be measured at 4, 8 and 12 weeks within each period in each sequence. Every 2 week VAS scores will be collected via phone at weeks 2,6,10 and in person at weeks 4, 8, 12. All secondary outcomes surveys will be done at a face to face visit at weeks 4, 8, 12.

Outcome measures: (RCT and substudy)

: Primary efficacy endpoint is the visual analog scale (VAS) score at the end of each of the three 12-week periods (at weeks 12 and 24). Secondary outcome measures include the Multidimensional Pain Inventory (MPI) Pain Severity Subscale, MPI-SCI, International SCI Pain Basic Data Subset (SCIPBDS), WHOQOL-BREF, Spinal Cord Independence Measure (SCIM) and number of concomitant pain medications

Specific Aims

- 1. Determine the effect of the capsaicin 8% patch on VAS scores.
- 2. Determine the effect of the 8% Capsaicin (C8P) on QOL.
- 3. Determine the effect of the C8P on physical function. .

UHS clinic sites: Patients will be approached by providers (who are also investigators in this study), regarding being contacted by phone to hear more about the study. If agreeable patient's name and phone number will be provided manually/verbally to the study team at the VA in order to contact interested patients. No PHI will be transferred electronically between UHS and the VA. Data for the study will be provided by patient and collected at the VA.

Data Analysis Plan:

RCT: Due to the small population of individuals with a spinal cord injury and high incidence of neuropathic pain in such persons and lack of prospective studies on the capsaicin 8% patch, we felt a small group of 25 patients was large enough to show possible potential benefits, small enough to realistically complete this study, follow patients appropriately according to standard of care, and in congruence with the small population size commonly seen in spinal cord injury studies. This study will serve as pilot data for a larger study in the future.

Substudy: Non-randomized, non-controlled arm: 50 participants will be enrolled and we will use the baseline and post patch application data to help determine the number needed to treat and minimal clinically important difference for the RCT.

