RCT and substudy: Data analysis will be performed on subjective description of pain at baseline from NPRS, VAS and evaluated at 2, 4, 8, 12 weeks post application to determine efficacy of capsaicin 8% patch in regards to point value and percentage of reduction compared to baseline. Longevity as recorded by reduction in baseline NPRS and VAS scores in days, weeks, and months of relief until pain returns to baseline. We will also compare our quality of life scale (WHO-QOL) and SCIM scores from pre study to post study and evaluate for more subjective measures of improvement in quality of life and functional improvement respectively. In the RCT trial we will assess for significant differences is outcomes between the treatment and control groups over time whereas, in the non-randomized, non-controlled trial we will compare baseline scores to 12 weeks post patch application scores for all outcomes. The significance of variation in the mean outcome with treatment will be assessed with a mixed effects linear model of the outcome in terms of sequence, subject nested in sequence, period, treatment, and first order carryover. All statistical testing will be two-sided with a significance level of 5%. SAS Version 9.4 for Windows or later, SAS Instititue, Cary, North Carolina, or R will be used throughout.

0

15-322H, [name], Form BC, 07-24-19, AMD.docx vSept3-2014

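### In the two-period AB/BA layout, the planned model with both sequence and carryover cannot estimate the treatment effect; dropping carryover understates C8P only if its relief persists into period 2

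*Combined protocol and SAP*

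**What the plan says.** **Design.** Item 2 gives a "Randomized dual balanced 2-sequence 2-treatment, 2-period (each period is 12 weeks long), crossover study". In Item 6, under Randomization, Table 1 shows sequences AB and BA (A is C8P, B the low-dose control patch), and the text adds: "Each treatment period will be 12 weeks in duration. The proposed design is a standard 2-period, 2-treatment, 2-sequence design". The primary endpoint (Item 6, Outcome measures) is VAS "at the end of each of the three 12-week periods (at weeks 12 and 24"), so period 2 starts where period 1 ends. Two pieces of wording conflict with this. The opening line under Randomization labels the design three-period, and the endpoint sentence counts three periods while listing two time points.

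**Separation of periods.** No section states a washout or makes the second patch depend on pain having returned. Return of pain to baseline appears only as a longevity outcome in the Data Analysis Plan. That plan does not say which baseline applies after the second patch.

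**Model.** The mixed linear model (Data Analysis Plan, paragraph for RCT and substudy) is written "in terms of sequence, subject nested in sequence, period, treatment, and first order carryover". The same paragraph says "we will assess for significant differences is outcomes between the treatment and control groups over time", and VAS is collected two-weekly: "Every 2 week VAS scores will be collected via phone at weeks 2,6,10 and in person at weeks 4, 8, 12".

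**Duration of relief.** Item 3 reports that three patients in a retrospective review "had complete relief of pain on average after 2 weeks for an average duration of 169 days". Item 4 expects that "a single topical application of the C8P for only 1 hour could potentially provide pain relief for 8-12 weeks".

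**The concern.** The carryover term is the only protection the plan offers against C8P relief running into period 2, and it is the term that breaks the model. With sequence also in the model, a two-period, two-sequence layout has too few distinct cell means to separate treatment from carryover. Software will either report treatment as non-estimable or drop a column. The two obvious repairs answer with different estimators. One is precise but open to carryover. The other is free of carryover but has about twice the standard error. A two-sided 5% test should not rest on an unwritten choice between them.

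The secondary worry is conditional. If carryover is dropped and C8P relief is still present at week 24 in Sequence 1, that relief counts as control response. The estimate then shrinks toward no difference. The Data Analysis Plan says that the trial will provide pilot data for a larger study, so a shrunken effect could pass into that study's planning.

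**Working it through.** There is no planned figure to reproduce. The 25 patients are justified by feasibility, without an effect size, SD or power.

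**1. Rank of the planned model.** Inputs are Table 1 and the model terms in the Data Analysis Plan, with ±1 coding.

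| Cell | Sequence | Period | Treatment | Carryover |
|---|---|---|---|---|
| Seq 1, period 1 (A) | 1 | 1 | 1 | 0 |
| Seq 1, period 2 (B) | 1 | −1 | −1 | 1 |
| Seq 2, period 1 (B) | −1 | 1 | −1 | 0 |
| Seq 2, period 2 (A) | −1 | −1 | 1 | −1 |

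In every row, carryover = (sequence − treatment)/2. With the intercept there are 5 columns of rank 4. Adding the row that isolates treatment raises the rank to 5, so treatment is not estimable. Fixed subject effects do not help (30 columns, rank 27), nor do the six two-weekly readings as time levels (10 columns, rank 9).

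**2. What each repair estimates.** Weights on the four cell means, in table order, for A minus B:

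- Carryover dropped: (1, −1, −1, 1)/2, the ordinary crossover contrast.
- Sequence dropped: (1, 0, −1, 0), the period-1 comparison between patients.

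**3. Attenuation with carryover dropped.** Let t be the week-12 effect and f the fraction of it still present at week 24 in Sequence 1, with negligible carryover from the control patch. Apart from period effects, which cancel, the cells expect t, ft, 0 and t. The contrast is ½(t − ft − 0 + t) = t(1 − f/2). In general the bias is half the difference between the two carryovers. A simulation with a true effect of −2 gave −1.99, −1.50 and −0.99 at f = 0, 0.5 and 1, which agrees with the formula. The period-1 comparison expects t whatever f is.

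**4. Values of f that the documents allow.** The Sequence 1 control endpoint falls 24 × 7 = 168 days after C8P.

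- Relief of 8 to 12 weeks (Item 4): f is about 0 and recovery about 100%.
- Mean of 169 days over three patients (Item 3), each either in relief or not: at least one duration must exceed 168 days. Among those still in relief at day 84, the fraction beyond day 168 can be 1/3, 1/2, 2/3 or 1. Durations of 160, 160 and 187 days (sum 507, mean 169) give f = 1/3 and recovery 1 − 1/6 = 83%. Durations of 60, 60 and 387 days (sum 507) give f = 1 and recovery 50%.

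**5. Earlier period-2 readings.** Relief that ends between weeks 13 and 23 leaves week 24 clean but lowers earlier Sequence 1 control readings. As an illustration, assume relief ends evenly over days 91 to 161. The proportions still in relief at days 98, 112, 126, 140, 154 and 168 are 0.90, 0.70, 0.50, 0.30, 0.10 and 0. Recovery at period weeks 2, 4, 6, 8, 10 and 12 is then 55%, 65%, 75%, 85%, 95% and 100%, a mean of 79%.

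**6. Precision.** Assume 13 v 12 patients, correlation 0.5 both within patient and with baseline, and units of the VAS SD. √(1/13 + 1/12) = 0.400.

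- Crossover SE: ½ × √(2(1 − 0.5)) × 0.400 = 0.20.
- Period-1 SE: 0.40 unadjusted; 0.40 × √(1 − 0.25) = 0.35 adjusted for baseline.
- Crossover root mean square error: √(0.20² + (df/2)²), where d = t/SD. At d = 0.8, f = 0.69 it is √(0.040 + 0.076) = 0.34, against 0.35 for the adjusted period-1 estimate. At d = 1.0, f = 0.69 it is √(0.040 + 0.119) = 0.40, against 0.35.

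**The case against.** **Three-period reading.** The same terms are estimable in a true three-period dual design such as ABB/BAA (6 columns, rank 6), and the leftover wording suggests that the carryover term may come from one. That may explain the error, but it does not rescue the model. Table 1, Item 2, the sentence calling the design a standard two-period one, and endpoints at weeks 12 and 24 all fix two periods.

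**Baseline as a response.** If pre-study VAS entered as an extra outcome row, the design would have rank 6 of 6. Treatment would then be the period-1 difference in change from baseline. This is a fair point, since the plan does analyse baseline pain. But it nowhere says that baseline is a response in this model, and using change from baseline as the outcome leaves the aliasing in place.

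**Relief may not persist.** On the 8 to 12 weeks of Item 4, relief is gone long before week 24 and the crossover contrast is essentially unbiased. This stands, and it makes the attenuation secondary.

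**It is a pilot.** This is true, and it limits the severity. The plan still specifies 5% testing and still intends the results to inform a larger study.

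**Conclusion.** The model fault is certain on the two-period design that the protocol describes, and it needs no assumption about capsaicin. Treatment is not estimable as written, so the result depends on an unstated choice of which term to drop. This should be fixed before analysis.

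The attenuation is conditional. With carryover dropped and negligible control carryover, the contrast recovers about 100% of t if relief lasts 8 to 12 weeks. It could recover 50% to 83% if the 169-day mean applied with all-or-none relief. Readings before week 24 in period 2 could be affected by shorter relief.

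A reader might infer that the trial will understate C8P, or that a definite shrinkage such as a quarter to a third should be expected. The documents do not support either. The 169 days is a mean over three patients with no spread, and any narrower band needs an invented distribution of durations. The 8 to 12 weeks in Item 4 is an equally available expectation. Nor does the missing washout alone bias the primary contrast: if no C8P relief remains at week 24, that contrast is unbiased.

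**What to change.** 1. In the Data Analysis Plan, remove first-order carryover and keep sequence, period, treatment and subject within sequence. Delete the three-period wording under Randomization and Outcome measures. State that the estimate is attenuated if C8P relief persists into period 2.
2. Prespecify the randomised period-1 week-12 VAS comparison adjusted for pre-study VAS, not triggered by a carryover test. Report it with its confidence interval beside the crossover, as the estimate free of carryover. Use both when planning the larger study.
3. Take the week-12 VAS before the second application, including its lidocaine/prilocaine pre-treatment. Report its mean difference from pre-study VAS by sequence.
4. Report reduction from pre-study baseline and longevity of relief for period 1 only, or flag period-2 values as not attributable to the second patch.

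**Cost.** Wording only, provided the second patch goes on at or after the in-person week-12 visit; the protocol does not state the day. No visit or measurement is added. I do not ask for a washout: it would lengthen the trial, and the documents give no spread of durations from which to set its length.

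**Downside.** The adjusted period-1 estimate is imprecise (SE about 0.35 SD, against 0.20 SD for the crossover, at assumed correlation 0.5) and cannot by itself show whether the crossover is biased. Keeping the crossover as the single 5% test is a precision choice. Its root mean square error is lower when the effect or its persistence is small, and higher when both are large.

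### The RCT's primary VAS is read only at week 12 of each period, the outer limit of the hypothesised 8–12 weeks of relief, so a patch that works as hypothesised can show little or no effect on the primary test

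*Combined protocol and SAP*

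**What the plan says.** - **Primary endpoint** (Item 6, Outcome measures): the "visual analog scale (VAS) score at the end of each of the three 12-week periods (at weeks 12 and 24"). The mention of three periods conflicts with the two time points and with the two-period layout in Table 1. That is a separate matter; on either count there is one reading per period.
- **Hypothesis** (Item 4): a "single topical application of the C8P for only 1 hour could potentially provide pain relief for 8-12 weeks".
- **Period length** (Item 6, Randomization): "Each treatment period will be 12 weeks in duration". No washout is described.
- **VAS schedule** (Item 6, Post patch application data collection): "Every 2 week VAS scores will be collected via phone at weeks 2,6,10 and in person at weeks 4, 8, 12". The abstract (Item 2) describes the primary outcome as measured every two weeks.
- **Analysis** (Item 6, Data Analysis Plan, RCT and substudy): pain scores are "evaluated at 2, 4, 8, 12 weeks post application to determine efficacy of capsaicin 8% patch". The same paragraph plans a description of how long relief lasts and, for the RCT, a treatment–control comparison over time. The mixed model contains sequence, subject within sequence, period, treatment and first-order carryover, with no term for week. For the substudy, the paragraph adds that "we will compare baseline scores to 12 weeks post patch application scores for all outcomes".

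**The concern.** Aim 1 is the effect of the 8% patch on VAS scores. The endpoint that decides it samples each period once, at the far end of the window in which the protocol expects relief. A patient whose pain is relieved from week 2 to week 10 and then returns to baseline behaves as the hypothesis predicts, yet contributes nothing to the primary contrast. Five of the six scheduled VAS readings per period do not enter it.

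With 25 patients, a number justified by feasibility, there is little room to lose signal. The other planned analyses could show the early benefit, but the plan does not say which result answers Aim 1 if they disagree with week 12.

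**Working it through.** **Inputs from the documents.** Primary readings at study weeks 12 and 24; VAS at weeks 2, 4, 6, 8, 10 and 12 of each period; hypothesised relief of 8–12 weeks; 12-week periods with no described washout; n = 25. The plan gives no effect size, SD or power, so there is no stated figure to reproduce.

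**Assumptions.** Relief is in place by week 2, constant while it lasts, and then ends. The control patch has no effect of its own. Duration is lognormal with CV 25%, 50% or 75%. The contrast is not adjusted for carryover. The documents give no distribution of duration, so these choices are mine.

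**Formulas.** Let e(t) be the share of patients still in relief t weeks after the 8% patch. In sequence 1 the active reading shows e(12), and the control reading 12 weeks later still carries e(24). In sequence 2 the active reading shows e(12) and the control reading carries nothing. Averaging the two sequences, the share of the full effect captured is:

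- week 12/24: e(12) − e(24)/2
- mean of weeks 2–12: mean of e(2), e(4), …, e(12), minus half the mean of e(14), e(16), …, e(24)

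**Worked case: mean 10 weeks, CV 50%.** The log variance is ln(1 + 0.5²) = 0.2231 (SD 0.4724) and the log mean is ln 10 − 0.2231/2 = 2.191.

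- e(2) to e(12): 0.999, 0.956, 0.801, 0.593, 0.407, 0.267; mean 0.670
- e(14) to e(24): 0.171, 0.109, 0.069, 0.044, 0.028, 0.018; mean 0.073
- week 12/24: 0.267 − 0.018/2 = 0.258, or 26%
- mean of weeks 2–12: 0.670 − 0.073/2 = 0.634, or 63%

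**Share of the full effect captured**

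| Mean duration (weeks) | Week 12/24, CV 25 / 50 / 75% | Mean of weeks 2–12, CV 25 / 50 / 75% |
|---|---|---|
| 8 | 4 / 13 / 16% | 58 / 54 / 48% |
| 10 | 19 / 26 / 25% | 73 / 63 / 55% |
| 12 | 45 / 38 / 33% | 82 / 69 / 60% |
| 24 | 77 / 69 / 57% | 62 / 67 / 65% |

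**Where the order reverses.** At CV 25% the two are level at about 16 weeks (83% each). Week 12/24 is then ahead to at least 26 weeks (71% against 58%). At CV 50% they are about equal from 22 weeks (68% against 69%). At CV 75% the average stays ahead through 26 weeks.

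**Check with a different duration model.** If duration is uniform on 8–12 weeks, the share in relief is 100% at weeks 2, 4, 6 and 8, 50% at week 10 and 0% at week 12. The six-visit mean is (4 × 100 + 50 + 0)/6 = 75%. If duration is instead normal with mean 10 weeks and 80–95% of patients within 8–12 weeks, 2.5–10% are still in relief at week 12 and the six-visit mean is again about 75%.

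**Check with one fixed duration.** At 10 weeks the shares are 0% at week 12 and 5/6 = 83% for the mean, counting a reading taken as relief ends as relief. By the same convention, a fixed 12 weeks gives 100% for both. A fixed 24.1 weeks gives 50% for both, because relief persists through the whole control period of sequence 1.

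**Variance.** The mean of six readings with common correlation r has (1 + 5r)/6 of the variance of one reading: 58% at r = 0.5 and 83% at r = 0.8 (assumed values).

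**Power, as illustration only.** This uses a two-sided 5% t test on within-patient differences with n = 25 and df = 23, under the uniform and normal duration models. Assume a full effect of 1.5 VAS points and an SD of differences of 2.5. Power is 5–6% at week 12 and 58% for the six-visit mean with the same SD. Over full effects of 1–2 points and SDs of 2–3, the ranges are 5–8% and 22–95%.

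**The case against.** The strongest reply is that the earlier readings are not discarded. The Data Analysis Plan evaluates pain at 2, 4, 8 and 12 weeks, describes how long relief lasts and compares the arms over time. Early relief that faded by week 12 would be visible there. This stands, and it rules out the tempting inference that a null primary result would be uninterpretable. What remains is narrower. None of these analyses is ranked as primary, weeks 6 and 10 are absent from the list, and the stated model has no week term.

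Second, relief may last longer than hypothesised. Item 3 cites a retrospective review of three patients with relief averaging 169 days (169/7 = 24.1 weeks). At that duration week 12 captures the active effect well and can beat the average, as the 24-week row shows for CV 25% and, slightly, CV 50%. This also stands, although three patients are weak evidence and the protocol's own hypothesis is 8–12 weeks.

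Third, a landmark at the end of the period is a legitimate choice for persistence. With no washout described, it is also the period-2 reading furthest from carryover. It tests whether relief is still present at week 12. To say it tests whether relief outlasts 12 weeks would go too far.

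Fourth, the meta-analysis definition in Item 3, ">30% improvement in pain lasting from 2-12 weeks", could mean improvement sustained through week 12. Such responders would still register at week 12, so this citation does not clearly favour an averaged endpoint, and I do not rely on it.

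Finally, CV 50% fits an 8–12 week hypothesis loosely: at a mean of 10 weeks it puts only 33% of patients within that range. For that reason the results are shown across CVs and checked against durations concentrated on 8–12 weeks. The direction is the same, except that under the convention above a fixed duration of exactly 12 weeks gives a tie.

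**Conclusion.** The point holds for the RCT primary endpoint. Under the duration spreads assumed, week 12/24 captures 4–45% of the effect for mean durations of 8–12 weeks, and the mean of weeks 2–12 captures 48–82%. The percentages depend on assumed distributions, on abrupt loss of relief and on an inert control. The direction within the hypothesised range depends little on them. Beyond about 16 weeks of mean relief with little spread, the advantage passes to week 12.

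Two further inferences are not supported. A reader might conclude that the pilot would hand too small an effect to the later trial. The documents say the study will serve as pilot data, but not that only the week 12 estimate is passed on. A reader might also conclude that the substudy looks at nothing but week 12. One sentence reads that way, but the opening of the same paragraph applies the 2, 4, 8 and 12 week evaluation and the duration description to the substudy too. The two statements need reconciling; they do not show that the earlier weeks are ignored.

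This is a change the sponsor should make, chiefly because it is cheap.

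**What to change.** - In Outcome measures, define the RCT primary endpoint as the mean of the six scheduled VAS readings (weeks 2–12) in each period. Keep the week 12 VAS as a secondary endpoint for persistence.
- Align the abstract, Outcome measures and the Data Analysis Plan, so that one summary is named primary and the time-course and duration analyses are labelled secondary.
- In the Data Analysis Plan, reconcile the substudy's week 12 comparison with the 2, 4, 8 and 12 week evaluation stated for it in the same paragraph.

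**Cost.** A few sentences, with no new visits or data. The mean still gives one value per patient per period, so the change itself adds no week term to the model. A rule for missed readings is needed. Phone and in-person readings are mixed, but in the same pattern in both periods.

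**Downside.** With no described washout, the early period-2 readings in sequence 1 carry more residual effect if relief lasts well beyond 12 weeks. At a mean of 24 weeks the average captures 62% against 77% for week 12/24 at CV 25%, and 67% against 69% at CV 50%. Reporting week 12 as secondary keeps that information available.

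### Longevity of relief runs until pain returns to baseline, but follow-up free of a second patch stops at week 12 and the plan has no rule for unfinished durations

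*Combined protocol and SAP*

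**What the plan says.** The measure is in Item 6, Data Analysis Plan, in the paragraph covering both RCT and substudy: "Longevity as recorded by reduction in baseline NPRS and VAS scores in days, weeks, and months of relief until pain returns to baseline". The sentence before it says pain scores are "evaluated at 2, 4, 8, 12 weeks post application". The only model named is a mixed linear model with terms for sequence, subject, period, treatment and carryover. No time-to-event method, censoring rule or definition of return to baseline is given.

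The observation window is set elsewhere in Item 6:

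- Randomization: "Each treatment period will be 12 weeks in duration".
- Methods, sequence 1: "C8P application followed by one reapplication of a low dose capsaicin control patch".
- Methods, substudy: "they will be followed for a 12 week period using the identical protocol of data collection post patch application in the RCT". The pre-study section says that nothing is collected beforehand in this arm.
- Post-patch data collection: "Every 2 week VAS scores will be collected via phone at weeks 2,6,10 and in person at weeks 4, 8, 12".
- Outcome measures: the primary VAS is read "at the end of each of the three 12-week periods (at weeks 12 and 24"). The word three conflicts with the two periods in Table 1. The weeks given fit two.

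The documents give two figures for how long relief might last. Item 3 cites a retrospective review of three patients, who had "complete relief of pain on average after 2 weeks for an average duration of 169 days". Item 4, the study's own rationale, hopes for 8 to 12 weeks from one application.

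**The concern.** The measure ends at an event that may fall outside the window. A patient still relieved at day 84 has no observed end of relief attributable to that patch alone. After C8P, sequence 2 and the substudy have no further scheduled contact, and sequence 1 goes on to a second capsaicin patch. A linear model needs a completed number for each patient, so the analyst would have to improvise. The two obvious choices are to enter 84 days or to leave the patient out. Both pull the average down, and leaving patients out removes the best responders.

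The units do not fit either. With two-weekly VAS, the end of relief is known only to lie between two contacts up to 14 days apart, so a result in days is finer than the data allow.

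Item 4 presents lasting relief from a single application as the novelty of the product, and the trial is described as pilot data for a larger study. A duration that is biased downward could be carried into that study.

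**Working it through.** **No plan figure to reproduce.** The 169 days is a cited average without patient-level data, and the plan has no calculation for longevity.

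**Inputs.**
- Window after each patch: 12 × 7 = 84 days (Item 6).
- Last RCT visit: 24 × 7 = 168 days (Item 6). It is reached after C8P only in sequence 1, with the control patch applied in between.
- Candidate true means: 8 × 7 = 56 and 12 × 7 = 84 days (Item 4), and 169 days (Item 3).
- Assumption: durations among patients with relief are exponential with mean m. The documents give no distribution.

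**Formulas**, with τ = 84:
- Still relieved at day 84: p = exp(−τ/m).
- Mean if unfinished durations are entered as 84: m(1 − p).
- Mean if unfinished durations are dropped: m − τp/(1 − p).

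**Results.**

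| True mean | p | Capped mean | Mean of completed durations only |
|---|---|---|---|
| 56 days | exp(−1.5) = 0.223 | 56 × 0.777 = 43.5 | 56 − 84 × 0.223/0.777 = 31.9 |
| 84 days | exp(−1) = 0.368 | 84 × 0.632 = 53.1 | 84 − 84 × 0.368/0.632 = 35.1 |
| 169 days | exp(−0.497) = 0.608 | 169 × 0.392 = 66.2 | 169 − 84 × 0.608/0.392 = 38.5 |

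Under the exponential, the capped mean falls short by the fraction p: 22%, 37% and 61%.

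**Sensitivity to shape.** Replacing the exponential by Weibull distributions with shape 1 to 4 and the same mean gives:

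| True mean | Still relieved at day 84 | Capped mean | Shortfall |
|---|---|---|---|
| 56 days | 3% to 22% | 44 to 56 days | 0.3% to 22% |
| 84 days | 37% to 51% | 53 to 75 days | 11% to 37% |
| 169 days | 61% to 96% | 66 to 83 days | 51% to 61% |

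**Denominator.** These shares apply to patients with relief. As an illustration only, take the 43% responder rate that Item 3 quotes from other pain populations. The unfinished share of all patients would then be 0.43 × 0.223 = 10%, 0.43 × 0.368 = 16% and 0.43 × 0.608 = 26%.

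**The case against.** Several stronger readings are tempting, and the documents do not support them.

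- A reader might infer that the protocol expects relief to last 169 days, so that the measure must fail for most patients. That figure is a background citation of three patients, all with complete relief. The protocol's own rationale is 8 to 12 weeks, inside or at the edge of the window. With a mean of 56 days and a favourable shape, the shortfall is only 0.3%.
- A reader might infer that nothing is observed after week 12. In sequence 1, VAS continues to week 24 after C8P. Those scores follow a low-dose capsaicin patch and cannot isolate C8P, but they exist.
- A reader might infer that the plan commits to a biased average. It does not say that durations will be averaged, capped or restricted to completed ones; it is silent. A capped mean is even a legitimate quantity if every patient is followed to week 12 and it is labelled as a mean restricted to 12 weeks.
- A reader might infer that the trial would misjudge the main advantage of the product. Whether relief persists at week 12 is addressed by the primary VAS endpoint, which does not depend on longevity. Longevity appears in neither the primary endpoint, the secondary outcome list nor the three aims.
- The list of weeks 2, 4, 8 and 12 belongs to the efficacy sentence. It does not show that longevity would be read at 4-week gaps.

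All of this lowers the size and priority of the point. It does not remove the mismatch between a measure that runs to return of pain and a design that stops at day 84.

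**Conclusion.** The point holds as a mismatch between measure and design. For anyone still relieved at week 12, longevity as defined cannot be delivered, and the two simplest ways of filling the gap both understate it. Under the exponential assumption, the capped mean is 22% to 37% too low if true mean duration matches the protocol's 8 to 12 weeks, and 61% too low if it were 169 days. Other shapes give 0.3% to 37% and 51% to 61%. These figures concern patients who have relief, and they apply only if unfinished durations are capped; dropping them is worse.

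Two related gaps must be closed at the same time. Return to baseline has no definition, and in period 2 it is unclear whether the reference is the pre-study score or the score at the start of that period. In the substudy, patients enrol after the patch and no pre-study data are collected, although the Data Analysis Plan speaks of using baseline data there.

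Priority is low to moderate. The primary endpoint is unaffected.

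**What to change.** Amend the Data Analysis Plan as follows.

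1. Define return to baseline and the reference score for each period.
2. Analyse longevity as time to return to baseline, right-censored at week 12 of the same period and interval-censored between contacts. Use all six VAS contacts, and NPRS at the times it is collected. Count patients who never have relief as zero, not missing.
3. Report by treatment the proportion still relieved at week 12 (Kaplan-Meier or Turnbull) and the restricted mean to 12 weeks. Add a within-patient comparison that respects the crossover, for example the difference in restricted duration between a patient's two periods.
4. State that sequence 1 period 2 scores do not extend C8P duration.
5. Do not report a mean duration in months.
6. Do not report return to baseline in the substudy unless a pre-patch score is available, and reconcile the two statements about baseline data in that arm.

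The cost is analysis-plan wording, with no added visits or patients. The downside is that relief lasting beyond the window is reported only as more than 12 weeks.
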